1.1. Objectives, Endpoints, and Estimands

Objectives	Endpoints
Primary	
Demonstrate noninferiority of LY3209590 compared to insulin degludec for the treatment of T2D in adults	Change in HbA1c from baseline to Week 52
Key Secondary (Multiplicity Adjusted)	
Demonstrate noninferiority of LY3209590 compared to insulin degludec for participants using GLP-1 receptor agonists	Change in HbA1c from baseline to Week 52
Demonstrate noninferiority of LY3209590 compared to insulin degludec for participants not using GLP-1 receptor agonists	Change in HbA1c from baseline to Week 52
Demonstrate superiority of LY3209590 compared to insulin degludec in selected parameters of glycemic control	
 • Change in HbA1c from baseline to Week 52 • Time in glucose range between 70 and 180 mg/dL (3.9 and 10.0 mmol/L), inclusive, collected during the CGM session prior to Week 52
Other Secondary	
 • Change from baseline to Week 26 of HbA1c • Time in glucose range between 70 and 180 mg/dL (3.9 and 10.0 mmol/L), inclusive, collected during the CGM session prior to Week 26 • Change from baseline to Week 26 and Week 52 of fasting glucose measured by SMBG • Glucose variability measured during the CGM session prior to Weeks 26 and 52 • Insulin dose at Weeks 26 and 52
Compare the effect of LY3209590 to insulin degludec on safety endpoints	
 • Incidence and rate of composite of Level 2 and 3 hypoglycemia events during treatment period • Incidence and rate of composite of Level 2 and 3 nocturnal hypoglycemia events during treatment period • Change from baseline to Weeks 26 and 52 in body weight • Measurements collected during CGM sessions prior to Weeks 12, 26, and 52 of

Objectives	Endpoints
	
 ○ Time in hypoglycemia with glucose <70 mg/dL (3.9 mmol/L) ○ Time in hypoglycemia with glucose <54 mg/dL (3.0 mmol/L) ○ Time in hyperglycemia defined as glucose >180 mg/dL (10.0 mmol/L)
Compare the effect of LY3209590 to insulin degludec on patient-reported outcomes questionnaires	
 • Change from baseline to Weeks 26 and 52 of 
 ○ TRIM-D ○ SF-36, and ○ EQ-5D-5L
Tertiary	
Compare the effect of LY3209590 to insulin degludec in participants using GLP-1 receptor agonists versus participants not using GLP-1 receptor agonists	
 • Rate of Level 1 and composite of Level 2 and 3 hypoglycemia events during the treatment period • Change from baseline to Weeks 26 and 52 in body weight • Insulin dose at Weeks 26 and 52 • Measurements collected during CGM sessions prior to Weeks 12, 26, and 52 of 
 ○ Time in hypoglycemia with glucose <70 mg/dL (3.9 mmol/L) ○ Time in hypoglycemia with glucose <54 mg/dL (3.0 mmol/L) ○ Time in hyperglycemia defined as glucose >180 mg/dL (10.0 mmol/L), and ○ Time in glucose range between 70 and 180 mg/dL (3.9 mmol/L and 10.0 mmol/L), inclusive
Compare the effect of LY3209590 to insulin degludec for efficacy parameters	
 • Percentage of participants at Week 52 achieving 
 ○ HbA1c <7% ○ HbA1c <7% without Level 2 or 3 nocturnal hypoglycemia, and ○ HbA1c \leq6.5% without Level 2 or 3 hypoglycemia • Change from baseline to Weeks 26 and 52 of fasting serum glucose
Compare the effect of LY3209590 to insulin degludec for safety parameters	
 • Incidence and rate of Level 2 hypoglycemia events during treatment period • Incidence and rate of Level 3 hypoglycemia events during treatment period • Evaluation of immunogenicity- incidence of positive LY3209590 treatment-emergent anti-drug antibodies
Characterize the PK/PD of LY3209590	
 • LY3209590 PK and concentration-response relationships to key safety and efficacy measures
Compare the effect of LY3209590 to insulin degludec for patient-reported outcomes	
 • SIM-Q and • Frequency of responses to Basal Insulin Experience of “likelihood of incorporating into routine”

Abbreviations: CGM = continuous glucose monitoring; GLP-1 = glucagon-like peptide-1; HbA1c = hemoglobin A1c; SMBG = self-monitoring of blood glucose; SF-36 = Short Form-36 Version 2 Health Survey Acute Form; SIM-Q = Simplicity Questionnaire; T2D = type 2 diabetes; TRIM-D = Treatment-Related Impact Measure – Diabetes.

Primary estimand (for primary objective)

United States registration

The primary clinical question of interest is: “What is the treatment difference between LY3209590 and insulin degludec in HbA1c change from baseline after 52 weeks of treatment, in study eligible participants, regardless of treatment discontinuation for any reason and regardless of initiation of rescue medication?”

The *treatment regimen estimand* will be used for the primary objective and the attributes are described in the following table.

Treatment Regimen Estimand Attribute	Description
Population	Targeted study population. See Section 3 for details.
Endpoint	HbA1c change from baseline to Week 52.
Remaining intercurrent events	None. The 2 intercurrent events, treatment discontinuation for any reason and initiation of rescue medication, are both addressed by the treatment condition of interest attribute.
Treatment condition	The randomized treatment regardless of treatment discontinuation and use of rescue medications.
Population-level summary	Difference in mean changes between treatment conditions.

Abbreviations: HbA1c = Hemoglobin A1c.

Rationale for estimand: the treatment regimen estimand estimates how participants with T2D are treated in clinical practice and considers both efficacy and safety.

Registration for countries outside the United States

The primary clinical question of interest is: “What is the treatment difference between LY3209590 and insulin degludec in HbA1c change from baseline after 52 weeks of treatment, in study eligible participants who adhere to the randomized treatment without intercurrent events during the study treatment period?”

The *efficacy estimand* will be used for the primary objective. This table describes the efficacy estimand attributes.

Efficacy Regimen Estimand Attribute	Description
Population	Targeted study population. See Section 3 for details.
Endpoint	HbA1c change from baseline to Week 52.
Remaining intercurrent events	None. The 2 intercurrent events, treatment discontinuation for any reason and initiation of rescue medication, are both handled by the hypothetical strategy, for example, the potential outcome for those participants if the intercurrent events have not occurred will be estimated.
Treatment condition	The randomized treatment.
Population-level summary	Difference in mean changes between treatment conditions.

Abbreviations: HbA1c = Hemoglobin A1c.

Rationale for estimand: the efficacy estimand supports the interpretation of the treatment effect as participants adhere to study treatment and free from the confounding effect of rescue medications.

Secondary estimands (for multiplicity-adjusted objectives)

The superiority test in change from baseline to Week 52 (Visit 31) in HbA1c will also be based on the primary estimand described above.

The change from baseline to Week 52 (Visit 31) in HbA1c in the subpopulations of participants using or not using GLP-1 receptor agonists will use treatment regimen estimand for US registration and efficacy estimand for other countries.

The time in glucose range between 70 and 180 mg/dL (3.9 and 10.0 mmol/L) inclusive measured during CGM session prior to Week 52 (Visit 31) will use treatment regimen estimated for US registration and efficacy estimand for other countries.

1.2. Study Design

- This is a Phase 3, parallel-design, open-label, randomized control study to evaluate the efficacy and safety of LY3209590 administered once-weekly compared to insulin degludec administered daily.
- The study includes a 3-week screening and lead-in period, a 52-week treatment period, and a safety follow-up period approximately 5 weeks after the last visit in the treatment period.
- Assignment to treatment groups will be determined by an interactive web-response system (IWRS). Participants will be randomly assigned to 1 of the 2 treatment groups in 1:1 ratio (LY3209590: insulin degludec) at Visit 3 (Week 0). The number of participants in each subpopulation of participants using or not using GLP-1 RA will be approximately 50% of the study population with balanced treatment assignment. Stratification will be by country, HbA1c stratum at Visit 1 (Week -3) (<8.0%, ≥8.0%), sulfonylurea use at randomization, and GLP-1 RA use at randomization, regardless of oral or injectable administration.
- Rescue therapy will be considered during the treatment period if the participants meet the protocol criteria of severe, persistent hyperglycemia.
- If study intervention is permanently discontinued, the participant will be encouraged to continue participation in the study for continued monitoring. Both efficacy (including HbA1c) and safety data will continue to be collected per the schedule of activities in the protocol.
- Participants will collect blinded CGM for 2 weeks prior to Visit 3 (Week 0), for 4 weeks prior to Visit 7 (Week 4), Visit 15 (Week 12), Visit 24 (Week 26), Visit 31 (Week 52), and for 4 weeks after Visit 31 (Week 52). Dexcom G6 system provides readings every 5 minutes. In China, instead of the Dexcom G6 system, the Libre Freestyle H system which provides readings every 15 minutes will be used. Main analyses for CGM measurements will be conducted based on data from the Dexcom G6 system.

2. Statistical Hypotheses

Primary Hypothesis

The primary objective of this study is to test the hypothesis that LY3209590 is not inferior to insulin degludec on glycemic control as measured by change in HbA1c from baseline to Week 52 (Visit 31) in participants with T2D who are starting basal insulin for the first time. The null hypothesis (H_0) is the difference between LY3209590 versus insulin degludec in the change from baseline to Week 52 (Visit 31) in HbA1c is greater than the noninferiority margin (NIM). The 2-sided 95% confidence interval (CI) will be used for testing the noninferiority.

Secondary Hypotheses

The key secondary objectives (multiplicity adjusted) are to test the hypotheses that LY3209590 is:

- not inferior to insulin degludec for change in HbA1c from baseline to Week 52 (Visit 31) for the subpopulation of participants using GLP-1 receptor agonists
 $H_0:$ the difference (LY3209590-insulin degludec) $>0.4\%$;
- not inferior to insulin degludec for change in HbA1c from baseline to Week 52 (Visit 31) for the subpopulation of participants not using GLP-1 receptor agonists
 $H_0:$ the difference (LY3209590-insulin degludec) $>0.4\%$;
- superior to insulin degludec for change in HbA1c from baseline to Week 52 (Visit 31)
 $H_0:$ the difference (LY3209590-insulin degludec) ≥ 0.0 ;
- superior to insulin degludec with respect to time in glucose range between 70 and 180 mg/dL (3.9 and 10.0 mmol/L), inclusive, collected during the CGM collected session prior to Week 52 (Visit 31)
 $H_0:$ the difference (LY3209590-insulin degludec) ≤ 0.0 .

[figure not shown]
These hypotheses and the primary hypothesis will be tested using a strategy to control the overall Type 1 error.

2.1. Multiplicity Adjustment

A graphical approach (Bretz et al. 2009; 2011) for multiple comparisons will be used to ensure the strong control of the overall type I error rate for testing the primary and key secondary (multiplicity adjusted) objectives. The overall significance level (α) will be set to 0.05. The total α will be used for the primary objective first, then the α will be allocated and transitioned to other key secondary objectives once the primary objective is met. Therefore, the noninferiority test for the primary objective will be based on the 2-sided 95% CI. Once the upper limit of the 2-sided 95% CI is below the NIM, the non-inferiority is achieved and the α of 0.05 will be distributed to conduct the tests for the key secondary objectives. If the p-value of the 2-sided test for one of the key secondary objectives is below the assigned α level, the objective is demonstrated and the assigned α level will be distributed to the remaining objectives. The iterative test procedure continues until none of the remaining objectives can be demonstrated with their preserved α or all objectives are demonstrated successfully. The NIM of 0.4% (for treatment regimen estimand) and 0.3% (for efficacy estimand) will both be tested to meet different regulatory requirements. No multiplicity adjustments will be made for conducting

separate analyses relative to the efficacy and treatment regimen estimands. Each estimand will have its own familywise error rate of 0.05.

For primary and key secondary efficacy objectives, the details of type I error control strategy are illustrated in [Figure 2.1](#). No multiplicity adjustments will be made for evaluating other secondary and exploratory objectives, or for safety assessments.

Primary: Change in HbA1c from baseline to Week 52
(LY3209590 noninferior to insulin degludec)

Key secondaries:

Change in HbA1c from baseline to Week 52

- for participants using GLP-1 RA;

- for participants not using GLP-1 RA;

(LY3209590 noninferior to insulin degludec)

Key Secondary: Change in HbA1c from baseline to Week 52 (LY3209590 superior to insulin degludec)

Key Secondary: Time in glucose range between 70 and 180 mg/dL (93.9 and 10.0 mmol/L), inclusive, collected during the CGM session prior to Week 52 (LY3209590 superior to insulin degludec)

Abbreviations: GLP-1 RA = glucagon-like peptide-1 receptor agonists; HbA1c= hemoglobin A1c;
NI = noninferiority; sup = superiority.

[Figure 2.1.](#)

Type 1 error control strategy for primary and key secondary efficacy endpoints.

3. Analysis Sets

The following analysis populations and data sets are defined for the purpose of analysis.

Analysis Populations/ Data Sets	Description
Entered Population	All participants who sign the informed consent form.
Randomized Population	All randomized participants. Participants will be analyzed according to the treatment they were assigned.
Modified Intent-to-Treat (mITT) Population	All randomized participants who took at least 1 dose of study treatment. Participants will be analyzed according to the treatment they were assigned.
Efficacy Analysis Set 1 (EAS1) for treatment regimen estimand on efficacy measures	
The data will include:
 
 • mITT Population excluding participants discontinuing the study treatment due to inadvertent enrollment; and • all measurements regardless of the use of study treatment or rescue medications.
Efficacy Analysis Set 2 (EAS2) for efficacy estimand on efficacy measures	
The data will include:
 
 • mITT Population excluding participants discontinuing the study treatment due to inadvertent enrollment; and • measurement up to the early discontinuation of study treatment or the initiation of rescue medication. 
The data cutoff for participants who had intercurrent events is defined by the earliest date from below dates for individual participants except for the analysis on study dose:
 
 • the date of last study dose + 10 days for LY3209590, or +1 day for degludec; and • the start date of the first rescue medication. 
The data cutoff for analysis on study dose is defined by the earliest date from below dates for individual participants:
 
 • the date of last study dose; and • the start date of the first rescue medication
Safety Analysis Set (SS)	
The data will include:
 
 • mITT Population; and • all measurement regardless of the use of study treatment or rescue medications
Continuous Glucose Monitoring (CGM) Primary Analysis Population	All randomized participants who use Dexcom G6 system for CGM data collection.

4. Statistical Analyses

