9.1. Statistical Hypotheses

Primary Hypothesis

The primary objective of this study is to test the hypothesis that LY3209590 is not inferior to insulin degludec on glycemic control as measured by change in HbA1c from baseline to Week 52 (Visit 31) in participants with T2D who are starting basal insulin for the first time.

The null hypothesis (H_0) is the difference between LY3209590 versus insulin degludec in the change from baseline to Week 52 (Visit 31) in HbA1c is greater than the NIM.

The NIMs of 0.4% and 0.3% will both be tested to meet regulatory requirements. The 2-sided 95% CI will be used for testing the noninferiority.

Secondary Hypotheses

The key secondary objectives (multiplicity adjusted) are to test the hypotheses that LY3209590 is

- not inferior to insulin degludec for change in HbA1c from baseline to Week 52 (Visit 31) for the subpopulation of participants using GLP-1 receptor agonists
 H_0 : the difference (LY3209590-insulin degludec) $>0.4\%$
- not inferior to insulin degludec for change in HbA1c from baseline to Week 52 (Visit 31) for the subpopulation of participants not using GLP-1 receptor agonists
 H_0 : the difference (LY3209590-insulin degludec) $>0.4\%$
- superior to insulin degludec for change in HbA1c from baseline to Week 52 (Visit 31)
 H_0 : the difference (LY3209590-insulin degludec) ≥ 0.0 , and
- superior to insulin degludec with respect to time in glucose range between 70 and 180 mg/dL (3.9 and 10.0 mmol/L) inclusive, collected during the CGM collected session prior to Week 52 (Visit 31)
 H_0 : the difference (LY3209590-insulin degludec) ≤ 0.0 .

These hypotheses and the primary hypothesis will be tested using a strategy to control the overall Type 1 error (see Section 9.1.1).

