4.3.2. Main analytical approach

The primary objective is to test the hypothesis that LY3209590 is noninferior to insulin degludec on glycemic control in the targeted study population. The noninferiority test will be based on either of the 2 estimands: **treatment regimen estimand** for the US FDA submission and **efficacy estimand** for registrations in other countries. The full significance level of 0.05 will be used for each estimand.

The following table provides the details of treatment regimen estimand and efficacy estimand.

	Treatment Regimen Estimand	Efficacy Estimand
Analysis Population	All participants in EAS1 with non-missing baseline measure	All participants in EAS2 with non-missing baseline measure and at least one non-missing post-baseline scheduled measure
Analysis Data	All non-missing observations at baseline and Week 52 (Visit 31) regardless of the use of study intervention or rescue medications.	All non-missing observations at baseline and all scheduled post-baseline timepoints during treatment period (that is, Weeks 2, 4, 12, 16, 26, 36 and 52) (prior to the date of last study dose + 10 days for LY3209590 (+1 day for degludec), or the initiation of rescue medication whichever is earlier for participants with intercurrent events).
Missing Data	There may be missing values at Week 52 (Visit 31) due to early study discontinuation. The missing values will be imputed using multiple imputation by the retrieved dropout approach. The retrieved dropout participants are those who discontinue study intervention prior to Week 52 but have non-missing measures at Week 52 in the same treatment arm. If there are only a limited number of retrieved participants that leads to a failure in performing the multiple imputation analysis, such as the model cannot converge, or the number of retrieved dropout participants is small (i.e., at least 1 arm has <8 participants who discontinued study treatment early and have endpoint visit measurements), the missing HbA1c at Week 52 will be imputed by return-to-baseline multiple imputation approach (Qu and Dai 2022)	There may be missing values due to the early discontinuation of study intervention or use of rescue medication. The MMRM model will be used, and the missing values will be handled in the MMRM analysis under the assumption of missing at random.

	Treatment Regimen Estimand	Efficacy Estimand

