Analysis Model	
After the imputation, the observed and imputed data will be analyzed by the ANCOVA model using treatment, strata (country, GLP-1 RA treatment at randomization, and SU use at randomization), and baseline value of the dependent variable as independent variables. The statistical inference will be based on the multiple imputation framework by Rubin (1987).
	
The MMRM model will include treatment, strata (country, GLP-1 RA treatment at randomization, and SU use at randomization), visit and treatment-by-visit interaction as fixed effects, and baseline of the dependent variable as a covariate. The Kenward-Roger approximation will be used to estimate denominator degrees of freedom for the MMRM models. An unstructured covariance structure will be used to model the within-participant errors. If this structure fails to converge, the following covariance structures will be used in order until one converges:
 
 1. Toeplitz with heterogeneity 2. autoregressive with heterogeneity 3. compound symmetry with heterogeneous variances 4. Toeplitz 5. Autoregressive 6. compound symmetry without heterogeneous variances.

Abbreviation: ANCOVA = analysis of covariance; MMRM = mixed model repeated measurement.

The 2-sided 95% CI of the LS mean difference (LY3209590 – insulin degludec) in the HbA1c change from baseline to Week 52 (Visit 31) will be estimated. For both estimands, LY3209590 will be declared noninferior to insulin degludec if the upper limit of the 2-side 95% CI for the LS mean difference in the HbA1c (measured in %) change from baseline is below NIM of +0.4%. In addition, the 95% CI for the LS mean difference will be compared to an alternative NIM of +0.3%.

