4.3.3. Sensitivity Analysis

4.3.3.1. Two-way Tipping Point Analysis

To confirm the robustness of the primary endpoint results, a 2-way tipping point analysis that represents varying assumptions for missing data from both treatment groups will be conducted. This sensitivity analysis will focus on missing data at the primary endpoint. Penalty parameters for imputed missing values will be added for both treatment arms. The ANCOVA model for treatment regimen estimand will be conducted after penalty parameters are added. The multiple imputation framework by Rubin (1987) will be used to summarize the results.

The corresponding p-value of non-inferiority test will be shown by color scale in the figure.

Additionally, imputation under the noninferiority null hypothesis will be conducted by adding 0.4 (NIM) to the imputed data using treatment regimen estimand (Section 4.3.2) for the LY3209590

group only. The ANCOVA model for treatment regimen estimand will rerun using the adjusted data. The multiple imputation framework by Rubin (1987) will be used to summarize the results.

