4.4.1.2. Main analytical approach

The non-inferiority test in change from baseline to Week 52 (Visit 31) in HbA1c for each of the subpopulations with participants using or not using GLP-1 RA will be analyzed. For the treatment regimen estimand (using data from the EAS1), for each subpopulation, the missing data will be imputed by multiple imputation with the approach similar to the imputation used for the primary endpoint. The imputed data for that subpopulation will be analyzed by the ANCOVA model using treatment, strata (country and SU use at randomization), and baseline HbA1c as independent variables. For the efficacy estimand (using data from the EAS2), the MMRM model which includes treatment, strata (country and SU use at randomization), visit and treatment-by-visit interaction as fixed effects, and baseline HbA1c as a covariate will be used, with data from that subpopulation.

The superiority test in change from baseline to Week 52 (Visit 31) in HbA1c will be based on the same primary endpoint analysis described in Section [4.3.2](#).

The time in glucose range between 70 and 180 mg/dL inclusive measured by CGM will be analyzed using an ANCOVA model for treatment regimen estimand and an MMRM model for efficacy estimand. CGM Primary Analysis Population will be used for the analyses. The analyses are similar to the primary analysis described in Section 4.3.2 with additional term of baseline HbA1c stratum ($<8.0\%$, $\geq 8.0\%$) in analysis models. For treatment regimen estimand, only participants with an observation at baseline or at Week 52 will be included in the analysis. the missing data at Week 52 will be imputed by multiple imputation with the approach similar to the imputation used for the primary endpoint. The missing baseline will be imputed using multiple imputation under assumption of missing at random.

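### For the efficacy estimand the SAP gives two different deciding noninferiority margins: 0.3% in Section 2.1 and 0.4% in Section 4.3.2

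*SAP*

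**What the plan says.** SAP Section 2.1 (Multiplicity Adjustment) links margin to estimand: "The NIM of 0.4% (for treatment regimen estimand) and 0.3% (for efficacy estimand) will both be tested to meet different regulatory requirements". It then makes the primary result the gate to the key secondary objectives: "Once the upper limit of the 2-sided 95% CI is below the NIM, the non-inferiority is achieved", after which the 0.05 is passed on.

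SAP Section 4.3.2 (Main analytical approach) gives the declaration rule: "For both estimands, LY3209590 will be declared noninferior to insulin degludec if the upper limit of the 2-side 95% CI" for the least-squares mean difference "is below NIM of +0.4%. In addition, the 95% CI for the LS mean difference will be compared to an alternative NIM of +0.3" (in %). Here 0.4% decides for both estimands, and 0.3% is an extra comparison tied to neither.

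Section 4.3.2 uses the efficacy estimand "for registrations in other countries. The full significance level of 0.05 will be used for each estimand", and Section 2.1 gives each estimand its own familywise error rate of 0.05.

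The protocol is neutral. Section 9.1 says "The NIMs of 0.4% and 0.3% will both be tested to meet regulatory requirements", and Section 9.3.2 gives +0.4% or +0.3% according to regulatory requirement. Neither links a margin to an estimand. The primary null hypothesis in SAP Section 2 carries no number.

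**The concern.** Both comparisons will be reported on either reading. What is undefined is which one is the primary verdict for the efficacy estimand, and so which one releases alpha. If the upper limit lands from 0.3% to below 0.4%, Section 4.3.2 declares the primary met, while under Section 2.1 it has failed and no key secondary may be tested.

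At most three key secondary tests turn on this: the two noninferiority tests by GLP-1 RA use, and superiority on time in range. HbA1c superiority does not, because "The superiority test in change from baseline to Week 52 (Visit 31) in HbA1c will be based on the same primary endpoint analysis", and an upper limit above 0 already fails it. The arrows of Figure 2.1 are not visible in the text, so the number could be lower.

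A gate at 0.4% controls error for a family headed by the 0.4% null. It does not do so for the 0.3% null that Section 2.1 assigns to this estimand. A choice between the two made after a borderline result would look like picking the margin that passes.

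**Working it through.** **Inputs (SAP Section 5; same in Protocol 9.5).** 377 completers per arm, SD 1.1%, true difference 0, two-sided 95% CI, margins 0.4% and 0.3%.

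**Standard error.** SE = 1.1 × √(2/377) = 0.0801; half-width = 1.96 × 0.0801 = 0.157.

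**The plan's own power.** P(upper limit < m | true difference d) = Φ((m − d)/SE − 1.96). At d = 0:
- m = 0.4: 99.9%, against at least 99% stated.
- m = 0.3: 96.3%, against at least 95% stated.

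A noncentral t calculation gives 99.88% and 96.24%. Both stated figures reproduce, so the sample size does not show which margin was meant to decide.

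**Where the sections disagree.** Both rules require the limit to be strictly below the margin. Section 2.1 passes when the estimate is below 0.3 − 0.157 = 0.143; Section 4.3.2 passes when it is below 0.4 − 0.157 = 0.243. An estimate of 0.20, for example, gives an upper limit of 0.357: failure under 2.1, success under 4.3.2.

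**How often.** The chance of disagreement is the power at 0.4% minus the power at 0.3%. Only d = 0 is the plan's noninferiority assumption; the other rows are assumptions made here.

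| True difference (%) | Pass at 0.4% | Pass at 0.3% | Disagree |
|---|---|---|---|
| −0.10 | 1.0000 | 0.9988 | 0.1% |
| −0.05 | 0.9999 | 0.9920 | 0.8% |
| 0 | 0.9988 | 0.9628 | 3.6% |
| +0.05 | 0.9920 | 0.8771 | 11.5% |
| +0.10 | 0.9628 | 0.7041 | 25.9% |
| +0.20 | 0.7041 | 0.2383 | 46.6% |

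If the SD differs from plan (also assumed here, with d = 0), the chance is 0.4% at SD 0.9 and 10.2% at SD 1.3.

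**Error at the 0.3% null.** With d = 0.3, the 0.4% rule opens the gate with probability Φ(0.1/0.0801 − 1.96) = 23.8%. The 0.3% rule does so 2.5% of the time.

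**The other estimand.** Sections 2.1 and 4.3.2 both use 0.4% for the treatment regimen estimand, and so does Section 4.3.3.1: "imputation under the noninferiority null hypothesis will be conducted by adding 0.4 (NIM) to the imputed data using treatment regimen estimand". That verdict is consistent throughout.

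**The case against.** The strongest reply is that both margins are tested for both estimands and each regulator applies its own. Protocol 9.3.2 supports this: its declaration rule covers both estimands and gives the two margins as alternatives. SAP Section 4.3.2 follows that sentence, and the SAP says the protocol analyses are unchanged. On this reading the parenthesis in Section 2.1 is the odd one out. That bears on which section to correct, but it does not name the margin that decides or that opens the gate.

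Several points on size stand:
- At the planned difference of 0 the conflict bites about 1 time in 28 (1/0.036). At the −0.3% used for the superiority power it is effectively nil.
- Only Section 2.1 describes the release of alpha. That the Section 4.3.2 verdict also opens the gate is an inference, though a direct one, since alpha moves once the primary objective is met.
- Three affected secondary tests is a ceiling. In the disputed zone the lower limit runs from 0.143 − 0.157 = −0.014 to 0.243 − 0.157 = +0.086, so time-in-range superiority is unlikely. With 188 per arm, the subpopulation half-width is 1.96 × 1.1 × √(2/188) = 0.222. Passing 0.4% then needs an estimate below about 0.178 even at full alpha. With equal halves, an overall estimate above 0.178 lets at most one subpopulation pass.
- The nulls are nested, so a claim at each margin, judged against its own null, keeps its 2.5% error. The 23.8% is an error rate only if 0.3% governs.

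These points limit the reach of the conflict. They do not reconcile the two sections.

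**Conclusion.** The concern holds. For the efficacy estimand, Sections 2.1 and 4.3.2 give opposite primary verdicts for any upper limit from 0.3% to below 0.4%. Neither the protocol, the SAP hypotheses, the sample size section nor the legible text of Figure 2.1 settles which applies. Under the plan's SD, completers and true difference of 0, the chance of landing there is 3.6%; it rises quickly if LY3209590 is slightly worse than degludec or the SD is larger than planned. The probability is modest, but this is the success rule for a primary estimand and it should be corrected. The US verdict is untouched. The documents do not show which margin was intended.

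**What to change.** Name one deciding margin for the efficacy estimand and use it in both sections. If Section 2.1 is right, replace the sentence covering both estimands in Section 4.3.2 with wording to this effect: *Noninferiority on the primary endpoint is concluded when the upper 95% confidence limit lies under +0.4% for the treatment regimen estimand, or under +0.3% for the efficacy estimand. That same margin opens the estimand's testing graph in Figure 2.1. The comparison with the other margin is reported but neither decides the primary nor releases alpha.* If +0.4% was agreed with regulators for the efficacy estimand, correct Section 2.1 instead. The 0.4% margin for the GLP-1 RA subpopulations needs no change.

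The cost is a few sentences of SAP wording, with no new data or participants. Power is 99.9% or 96.3%, so the stated sample size serves either choice. SAP version 3 says it was approved before final database lock; the documents do not show whether lock has since occurred. If it has, the study report should state the deciding margin and the pre-lock agreement it rests on.
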